7.13 Participation Endpoints of the Study

A patient's participation in the study will end after any of the following:

- Completion of all scheduled clinical and imaging evaluations to 1 month post-retrieval or 2 years post-placement;
- Device not implanted;
- Patient withdrawal or lost to follow-up;
- Closure of the study; or
- Patient death.

Any data collected on the patient up to a participation endpoint (or until all queries involving the patient are resolved) may be used in the study.

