6.3.2 Primary Safety Endpoint

The primary safety endpoint is the rate of 12-month freedom from major adverse events. Major adverse events are defined as: clinical perforation, clinical migration, clinical fracture, embolization of the filter or filter fragments to the heart or lungs, IVC thrombotic occlusion, new symptomatic DVT while a filter is indwelling, access site complications with clinical sequelae, and procedure-/device-related death. Analysis of the primary safety endpoint will be performed separately for each filter type (i.e., each stratum).

Events occurring after filter retrieval (i.e., through the 1-month post-retrieval follow-up period) will be collected, but only the events of access site complications with clinical sequelae and procedure-related death will count against the primary safety endpoint. Other events (i.e., potentially new DVT without symptoms) will be reported as a secondary measure.

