7.2 Point of Enrollment

Patients will be considered enrolled in the study once the filter introducer sheath is inserted below the skin.

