7.10 Duration of Study and Patient Participation

Patients will be followed until 1 months after successful filter retrieval or until study completion 2 years after filter placement. Total study duration (from study initiation through patient enrollment and follow-up) is expected to be less than 5 years.

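### Enrolled patients left without a filter exit with no observation period, so delayed procedure-related major adverse events can be missed by the primary safety endpoint

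*Combined protocol and SAP*

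**What the plan says.** - **Enrolment (7.2).** "Patients will be considered enrolled in the study once the filter introducer sheath is inserted below the skin". An attempt abandoned after that moment involves a study patient.
- **Exit (7.13).** "A patient's participation in the study will end after any of the following", and the list includes "Device not implanted". No minimum observation is attached. On data use, the section adds (last word omitted): "Any data collected on the patient up to a participation endpoint (or until all queries involving the patient are resolved) may be used in the".
- **Follow-up (7.7, 7.9, 7.10, Table 6.1).** Every scheduled contact after the procedure is tied to a filter having been placed or retrieved. Section 7.10 puts it as: "Patients will be followed until 1 months after successful filter retrieval or until study completion 2 years after filter placement".
- **Primary safety endpoint (6.3.2).** The major adverse events include "access site complications with clinical sequelae, and procedure-/device-related death". Appendix C defines the death component to cover the placement procedure as well as the filter. It defines the access-site component by transfusion, hospitalization or further treatment.
- **After retrieval (6.3.2).** Through the 1-month visit, "only the events of access site complications with clinical sequelae and procedure-related death will count against the primary safety endpoint".
- **Tested population (1.0, 8.1, 8.1.2).** Strata follow the filter type received, and the hypotheses are tested in patients receiving a Celect filter. No analysis set says where an enrolled patient with no filter belongs.

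**The concern.** Two components of the primary safety endpoint arise from venous access and the procedure, and neither needs an implant. Both can appear after the procedure day: a hematoma can lead to a later admission, and a death attributable to the procedure can come days afterwards. For a patient whose filter has been retrieved, the plan accepts that these harms belong in the endpoint without a filter and schedules a visit at 30 ± 15 days. For a patient whose filter was never implanted, it schedules nothing.

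What is at stake is completeness of the safety endpoint in a single-arm study judged against a fixed goal. If such a patient is event-free at exit, the Kaplan-Meier analysis either censors the patient near day 0 or, on the wording of 8.1, may leave the patient out altogether. In both cases a later procedural event is not seen.

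**Working it through.** **1. The plan's own figure.** Section 8.3 gives 88 patients for safety: 80% against 92.2%, one-sided exact binomial, type I error 0.025, power 0.9. At n = 88 the smallest rejecting count is 78. Then P(X ≥ 78 | 0.80) = 0.0238 and P(X ≥ 78 | 0.922) = 0.919, and 88 is the first n to reach 0.90. With 72% attrition, 320 × 0.28 = 89.6, which covers 88. The figure reproduces, and this point does not change it.

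**2. Who is affected.**

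| Enrolled patient | Scheduled contact after the procedure | Two procedure-related components captured later? |
|---|---|---|
| Filter implanted, placement successful | 3 months onward (7.7) | Yes |
| Filter implanted, technical placement failure (e.g. deformation) | 3 months onward (7.7) | Yes |
| Filter successfully retrieved | 1 month post-retrieval (7.9) | Yes, by 6.3.2 |
| No filter implanted | None (7.13) | Not by any scheduled contact |

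**3. Is there a rate in the documents?** Table 4.3 gives 0.14% against placement success, which reads as a failure rate: 41 + 554 + 129 = 724 patients, and 1/724 = 0.14%. Section 4.0 describes that event as a misplacement and migration with immediate retrieval and placement of a new filter. The patient ended with a filter, so 0.14% is not a non-implantation rate. The 5–23% for insertion problems in Table 4.1 is a class-wide figure with mixed definitions, and nothing says how many of those ended without an implant. A rate *f* therefore has to be assumed.

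**4. Size.** Expected number = 320 × *f*. Let *q* be the share of these patients with a missed event within the month, and *e* the 30-day event share in implanted patients. Take 92.2% as the 12-month rate in implanted patients and treat other early censoring as uninformative. Keeping non-implanted patients at risk to day 30 changes the pooled 30-day event share from *e* to (1 − *f*)*e* + *f q*. The 12-month rate then falls by

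*f* × (*q* − *e*) × 0.922 / (1 − *e*).

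In the worst case *q* = 1, and this is *f* × 0.922 whatever *e* is.

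| Assumed *f* | Expected of 320 | Worst-case overstatement (*q* = 1) | Exact power at n = 88 in that case |
|---|---|---|---|
| 0.5% | 1.6 | 0.46 points | 0.89 |
| 1% | 3.2 | 0.92 points | 0.86 |
| 2% | 6.4 | 1.84 points | 0.77 |

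With all 320 evaluable, power stays above 0.999 in every row. For a given *q*, the fall is largest when *e* = 0, where it equals *f q* × 0.922. At *f* = 2% it exceeds 1 point only if *q* is above 1/1.844 = 54%. The margin between assumption and goal is 92.2 − 80 = 12.2 points.

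**5. Direction.** The sign is that of *q* − *e*. Each missed event raises the reported rate. If these patients had fewer events than implanted patients in the first month, however, keeping them at risk would raise the estimate. With *q* = 0, *f* = 1% and an assumed *e* = 2%, the rise is 0.01 × 0.02 × 0.922 / 0.98, about 0.02 points. The documents give neither *q* nor *e*.

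**The case against.** The strongest opposing case is that this group may be close to empty. Section 7.5 requires imaging before enrolment to check anatomical criteria, so known anatomical obstacles should be found before the sheath goes in. The account of the prior studies in Section 4.0 describes no patient left without a filter. That stands, and it is why the size is small.

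It can also be said that adverse event reporting in 12.2 has no cut-off at exit. True, but it sets no reporting period beyond exit either, and 7.13 limits usable data to what was collected up to exit or until queries are resolved. No one is asked to look for later events.

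A third argument is that implanted patients have no 1-month visit either, since their first scheduled visit after discharge is at 3 months. That is correct, and the retrieval visit follows a different procedure. But implanted patients remain in the study, and the 3-month visit asks about hospitalizations and medical conditions. A non-implanted patient has no later contact at all.

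A reader might also infer three stronger things that the text does not support:

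- **That patients leave at once.** Section 7.13 gives no exit time. Immediate exit is an inference from the absence of any later contact, and events during the procedure are usable.
- **That all failed placements go unfollowed.** Those with a filter in place keep the normal schedule.
- **That the bias is always favourable.** Step 5 of the working shows that it need not be.

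**Conclusion.** The gap is real and narrow. Followed as written, the plan has no means of detecting access-site complications with clinical sequelae or procedure-related deaths that appear after exit in an enrolled patient with no filter. It does count those events for a month after retrieval. The analysis population for such a patient is also undefined.

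At an assumed non-implantation rate of 0.5% to 2%, about 2 to 6 of 320 patients are affected. The effect on the 12-month rate is probably under 1 point; the bound of 1.84 points needs both the 2% rate and a missed event in every such patient. This does not threaten the sample size and is unlikely to change the comparison with 80%. The size rests on assumed rates, on assigning these patients to the Celect stratum, and on the 92.2% planning figure. The change is worth making because it is cheap and because a stated rule can lose primary-endpoint events.

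**What to change.** - **7.13:** qualify the item "Device not implanted" by adding *after a 1-month (30 ± 15 days) post-procedure contact*.
- **7.10 and Table 6.1:** add that contact for enrolled patients with no implant. A telephone call suffices. It records the two procedure-related components: access-site complications with clinical sequelae and procedure-related death.
- **1.0, 8.1 and 8.1.2:** state that an enrolled patient without an implant is assigned to the stratum of the filter attempted and stays in the Kaplan-Meier safety risk set until that contact. Without this, the wording that limits strata and tests to patients receiving a filter could still keep the new data out of the test.

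The cost is a few extra calls, a few lines of protocol text and possibly a slightly less favourable major adverse event rate. The sample size does not change.

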8.0 Statistical Considerations

8.1 Hypotheses to be Tested

The study hypotheses will be tested only for patients receiving Celect[®] filters. No formal hypotheses will be tested for patients receiving the Günther Tulip[®] filter; rather, summary statistics will be presented for patients receiving the Günther Tulip[®] filter.

8.1.1 Primary Effectiveness Hypothesis

The primary effectiveness endpoint is the rate of technical placement success and 12-month freedom from new symptomatic PE while a filter is indwelling. The analysis requires that the performance goal of 90% be met for technical placement success and freedom from new symptomatic PE at 12 months while a filter is indwelling. The

performance goal was derived based on what are considered clinically acceptable rates for technical placement success and new symptomatic PE in the overall population.⁴⁸ The performance goal will be said to have been met provided the null hypothesis is rejected in favor of the alternative with a one-tailed exact binomial test at the 0.025 level. The hypothesis will be tested only for patients receiving Celect[®] filters. Given that π is the probability that a randomly selected patient did not experience any technical placement failure or new symptomatic PE within 12 months while a filter is indwelling, the null and alternative hypotheses are as follows.

Null Hypothesis: The rate of technical placement success and 12-month freedom from new symptomatic PE while a filter is indwelling, π , does not meet the performance goal (90%).

$$H_0: \pi \leq 90\%$$

Alternative Hypothesis: The rate of technical placement success and 12-month freedom from new symptomatic PE while a filter is indwelling, π , meets the performance goal (90%).

$$H_a: \pi > 90\%$$

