Recently, the SVS/SIR physician working group presented what they consider to be the clinically-acceptable 1-year event rates for filter-related safety and effectiveness

outcomes (Table 4.2). As detailed below, Cook's IVC filter data is favorable in comparison to the rates in Tables 4.1 and 4.2. Finally, these rates were utilized in the development of the performance goals and sample size for this study (described in further detail in Sections 8.1 and 8.3).

Table 4.2. Clinically-acceptable 1-year event rates⁴⁸

Adverse Event	Acceptable 1-Year Rate
Freedom from PE and procedural technical success	90%
Freedom from perforation, embolization, caval thrombosis/occlusion, DVT, major procedure related complications	80%
Caval Thrombosis/Occlusion	< 5%
Perforation	< 2%
DVT	< 5%
Embolization	< 2%
Fracture	< 5%
Migration	< 4%
Tilt	< 5%
PE	< 2%

Cook's IVC Filter Data

Cook Incorporated has sponsored three prospective, multi-center, single arm clinical studies of Cook IVC filters that are currently marketed in the US. Briefly, these include the IDE study of 41 US patients treated with the Günther Tulip[®] filter (G000242; results of which supported a retrievable indication, cleared in K032426), a second study of 554 US patients treated with the commercially available Günther Tulip[®] filter, and a study of 129 OUS patients treated with the Celect[®] filter (interim results of which supported permanent and retrievable indications). Results from all three studies have been published in peer-reviewed journals.¹⁻³

All three studies evaluated filter safety and effectiveness (outcome measures similar to those listed in Tables 4.1 and 4.2) in patients at risk for developing a PE; as such, a variety of reasons for filter placement are captured in the studies. Approximately half of the filter placements in these studies were associated with bariatric procedures or trauma cases; specifically, 28/41 patients (68.3%) in the IDE Günther Tulip[®] study, 329/554 patients (59.4%) in the second Günther Tulip[®] study, and 53/129 patients (41.1%) in the

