8.1.2 Primary Safety Hypothesis

The primary safety endpoint is the rate of 12-month freedom from major adverse events. Major adverse events are defined as: clinical perforation, clinical migration, clinical fracture, embolization of the filter or filter fragments to the heart or lungs, IVC thrombotic occlusion, new symptomatic DVT while a filter is indwelling, access site complications with clinical sequelae, and procedure-/device-related death. The analysis requires that the performance goal of 80% be met for freedom from major adverse events at 12 months. The performance goal was derived based on what are considered clinically acceptable rates for each complication in the overall population.⁴⁸

The null (H_0) and alternative (H_A) hypotheses are expressed as follows:

$$H_0: S(t) \leq 80\%$$

$$H_a: S(t) > 80\%$$

where:

- t is time through 12 months
- $S(t)$ is the true rate of freedom from major adverse events at time t .

The hypothesis will be assessed using a Z-statistic. The Z-statistic is given by

$$Z = (\hat{S}(t) - 0.8)/SE$$

where:

- $\hat{S}(t)$ = Kaplan-Meier estimate of freedom from major adverse events ($S(t)$) at 12 months
- SE = Standard Error = $\sqrt{V(S(t))}$, where $\hat{V}(\hat{S}(t))$ is the estimate of the variance of the Kaplan-Meier estimate using the methods described by Peto et al.⁵⁰

The performance goal will be said to have been met provided the null hypothesis is rejected in favor of the alternative if $\hat{S}(t) - 0.8 > Z_{\alpha}SE$, for $\alpha = 0.025$. The hypothesis will be tested only for patients receiving Celect[®] filters.

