8.3 Sample Size

The study is designed to enroll 320 patients in the Celect[®] filter stratum (to evaluate the safety and effectiveness hypotheses) and up to 150 patients in the Günther Tulip[®] filter stratum at up to 40 sites globally. At least half of the study patients in the Celect[®] filter stratum will be enrolled at US sites.

For the primary effectiveness endpoint, based on what are considered clinically acceptable rates for technical placement success and new symptomatic PE in the overall

population, a performance goal of the rate of technical placement success and 12-month freedom from new symptomatic PE while a filter is indwelling was established to be 90%.⁴⁸ Additionally, based on the data from previous Cook sponsored studies (as summarized in Section 4.0), the rate of technical placement success and 12-month freedom from new symptomatic PE while a filter was indwelling was estimated to be 98.4% for the Celect[®] filter stratum. A sample size of 70 patients will be required to assess the primary effectiveness hypothesis for the Celect[®] filter stratum, with a one-sided exact binomial test, at a type I error rate of 0.025, and a power of 0.9. The calculation was performed with the SAS UnifyPow macro.

For the primary safety endpoint, based on what are considered clinically acceptable rates for each complication in the overall population, a performance goal of the rate of 12-month freedom from major adverse events was established to be 80%.⁴⁸ Based on the data from previous Cook-sponsored studies (as summarized in Section 4.0), the rate of 12-month freedom from major adverse events was estimated to be 92.2% for the Celect[®] filter stratum. A sample size of 88 patients will be required to assess the primary safety hypothesis for the Celect[®] filter stratum, with a one-sided exact binomial test, at a type I error rate of 0.025, and a power of 0.9. The calculation was performed with the SAS UnifyPow macro.

Based on sample size calculations, a minimum of 88 patients in the Celect[®] filter stratum will be required to evaluate the safety and effectiveness endpoints. Cook intends to enroll 320 patients in the Celect[®] filter stratum; this sample size allows for an attrition rate of 72% (i.e., 60% of filters to be retrieved prior to 12 months and an additional 12% of patients who may die, withdraw, or become lost to follow-up). The study may also enroll up to 150 patients in the Günther Tulip[®] filter stratum.

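### The 90% effectiveness goal is a 1-year rate, but the exact binomial test takes no account of time with the filter in place, and Sections 8.1.1 and 8.3 imply different denominators for retrieved patients

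*Combined protocol and SAP*

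**What the plan says.** All references are to the combined protocol and SAP.

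- **Goal.** Section 8.1.1: "The analysis requires that the performance goal of 90% be met for technical placement success and freedom from new symptomatic PE at 12 months". Sections 8.1.1 and 8.3 take the 90% from the same source as Table 4.2 in Section 4.0. That table gives "clinically-acceptable 1-year event rates" and puts 90% against "Freedom from PE and procedural technical success". The same table has a separate limit for PE alone, below 2%.
- **Tested quantity.** In Section 8.1.1, π is the chance that someone drawn at random from the study population "did not experience any technical placement failure or new symptomatic PE within 12 months while a filter is indwelling". Section 6.3.1 excludes PE after retrieval from the endpoint and reports it as a secondary measure. Section 7.10 ends follow-up 1 month after a successful retrieval.
- **Test.** A "one-tailed exact binomial test at the 0.025 level", in Celect patients only.
- **Expected exposure.** Section 8.3 allows for "60% of filters to be retrieved prior to 12 months and an additional 12% of patients who may die, withdraw, or become lost to follow-up", and adds the two to a 72% attrition rate.
- **Safety, for comparison.** Section 8.1.2 bases its test on the "Kaplan-Meier estimate of freedom from major adverse events" at 12 months.
- **General provisions.** Section 8.2 foresees survival methods where data are censored, without tying them to a named endpoint. Section 8.4 makes case deletion the primary method for missing data while the sample stays large enough.

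**The concern.** A 1-year benchmark is compared with a crude proportion whose exposure time depends on when sites remove filters. As π is worded, a patient whose filter comes out PE-free after a few weeks earns the same credit as one who carries it PE-free for 12 months. Section 8.3 instead removes retrieved patients as attrition. Nothing in the plan says which of these the effectiveness analysis will do.

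The choice affects both error rates. If retrieved patients count as successes, a filter that only just sits at 90% over a full year in place can pass more often than 2.5% of the time, and more so with earlier retrieval. If event-free retrieved patients are dropped while failures stay in, the test becomes very conservative and a good filter may fail. The choice should be fixed before the data are seen.

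**Working it through.** **1. The plan's own sample sizes.** Exact binomial, one-sided 0.025.
- Effectiveness: goal 0.90, expected 0.984, n = 70. Pass at 68 or more successes; level 0.0242, power 0.898 (stated 0.9).
- Safety: goal 0.80, expected 0.922, n = 88. Pass at 78 or more; level 0.0238, power 0.919.

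Both reproduce.

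**2. Candidate denominators.** All enrolled: 320. After the 12% other loss: 320 × 0.88 ≈ 282. After 72% attrition: 320 × 0.28 = 89.6. The rule passes at 299 of 320 (at most 21 failures, level 0.0206) or 264 of 282 (level 0.022).

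**3. Retrieved patients counted as successes.** Let q be the probability of placement success and S(t) the PE-free probability with the filter in place. Set q × S(12) = 0.90, so the full-year with-filter rate is exactly at the goal, with constant hazard λ = −ln S(12)/12 per month. With 60% retrieved at time r:

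π = q × [0.4 S(12) + 0.6 S(r)]

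Section 4.0 gives mean indwell times of 179 days (prior Celect retrieval arm; 5.88 months) and 58.9 days (second Günther Tulip study; 1.94 months).

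Worked case, PE near Table 4.2's 2% limit (q = 0.92): S(12) = 0.90/0.92 = 0.9783 and λ = 0.00183. At 179 days S(r) = 0.9893, so π = 0.92 × (0.3913 + 0.5936) = 0.9061, and the chance of at least 299 successes in 320 is 4.5%. At 58.9 days π = 0.9100 and the chance is 7.3%.

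With q = 0.95 (about half the failures are PE), π = 0.9151 and 0.9251, giving 12.6% and 30.7%.

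These figures assume no other loss. Simulations with n = 320, 60% retrieved and 12% otherwise lost give the last two columns. Retrieval times there run from uniform over the year (mean about 182 days, close to the Celect figure) to a mean near 59 days.

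| Failures at the 90% goal (points) | Formula, n = 320: 179 d / 58.9 d | Simulated, event-free lost patients count as successes | Simulated, event-free lost patients deleted (8.4) |
|---|---|---|---|
| 8 placement, 2 PE | 4.5% / 7.3% | about 5–8% | about 1–2% |
| 5 placement, 5 PE | 12.6% / 30.7% | about 15–38% | about 4–15% |

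If PE is front-loaded (times averaging about a month), both rows of the n = 320 simulation fall to about 2–7%.

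**4. Retrieved patients removed.**
- Only patients carrying the filter for 12 months analysed: chance of passing at a true 90% is 1.8% (n = 89) or 1.7% (n = 90). There is no inflation.
- Event-free retrieved and lost patients dropped, all failures kept: chance at a true 90% is near zero, and power suffers. Take 98.4%, the sponsor's 0.14% placement failure (Table 4.3), constant hazard and uniform retrieval and loss. Successes: 320 × 0.28 × 0.984 ≈ 88. S(12) = 0.984/0.9986 = 0.9854, with average 0.9927 over uniform exit times. Expected failures: 320 × [1 − 0.9986 × (0.28 × 0.9854 + 0.72 × 0.9927)] ≈ 3.4. At about 90 patients the rule allows 3 failures (87 of 90). Simulated power is about 0.54, rising to about 0.75 with retrieval near 59 days.

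**5. Kaplan-Meier alternative.** All 320 enrolled, placement failure at day 0, censoring at retrieval, death or exit, pass if the one-sided 97.5% complementary log-log lower bound exceeds 90%. In the same scenarios the simulated level is about 1.5–3.4% and power about 0.95–0.996 at true rates of 98.0–98.4%. A plain Z-test against 0.90 on the same estimate, with constant hazard, runs at about 0.2–4% with the Peto standard error of 8.1.2 and about 5–6% with Greenwood's.

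**The case against.** Restricting the endpoint to time with the filter in place is a deliberate and disclosed choice, and for π as worded the exact binomial test keeps its level at or below 2.5%. That stands: the test is valid for the quantity it names. The issue is whether that quantity matches a 1-year benchmark, and who is in the denominator.

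A reader might infer that a filter at the goal could pass more than 90% of the time. The arithmetic can be made to give this (91% at n = 320), but only if nearly all of the 10 failure points are PE and retrieval follows the Günther Tulip indwell time. Table 4.2's own PE limit is below 2%, the sponsor's studies saw 1.1%, and only Celect is tested. The documents do not support that as a realistic size.

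A reader might also infer that the goal covers any PE at any time in the year, so that the endpoint counts only a subset of the benchmark's events. Table 4.2 is silent on time after retrieval and on symptoms, and Section 8.1.1 says the goal derives from acceptable rates of new symptomatic PE. Silence does not establish that mismatch.

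Section 8.3 can be read as analysing only 12-month carriers, which removes the inflation. But 8.1.1 refers to a randomly selected patient, and no section restricts the effectiveness analysis in this way. Section 8.2's sentence on survival methods names no estimator or censoring rule for this endpoint and leaves the pass rule of 8.1.1 in place.

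**Conclusion.** The concern holds as a gap in the definition of the effectiveness analysis. The goal is a 1-year composite, the test ignores time with the filter in place, and 8.1.1 and 8.3 point to different treatment of the 60% expected to be retrieved. Depending on that unwritten choice, the same test ranges from very conservative and underpowered to moderately lenient against the full-year with-filter rate.

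The case closest to the documents, PE at the table's 2% limit, gives about 5–8% at n = 320 and no inflation once event-free lost patients are deleted. Larger figures require PE above that limit. All of them rest on assumptions the plan does not supply: the PE share of failures, the timing of retrieval and the shape of the PE hazard. The power loss under the dropping rule does not need an extreme PE rate, since it arises at the plan's own 98.4%; the 0.54–0.75 assumes a constant hazard and almost no placement failures.

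**What to change.** In Section 8.1.1, test the 90% goal on the 12-month Kaplan-Meier estimate in all enrolled Celect patients. Count technical placement failure as an event at day 0 and new symptomatic PE with the filter in place as an event; censor at retrieval, death or exit. Declare the goal met if the one-sided 97.5% complementary log-log lower bound exceeds 90%. Specify that bound explicitly, because the Z forms in step 5 hold their level less well. Keep the exact binomial proportion as a descriptive secondary, with its denominator stated, and align the attrition wording and sample-size basis in 8.3 with the new rule.

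The cost is text in 8.1.1 and 8.3. No new visits or data are needed: time to retrieval and PE before and after retrieval are already collected. Power stays above the stated 0.9 in the scenarios simulated. The downsides are a somewhat wider interval, a level that can slightly exceed 2.5% in some scenarios, and the assumption, which a safety analysis censored at retrieval also makes, that censoring is non-informative. That is open to question because the assessed need for filtration guides retrieval (Section 7.7). The estimate still does not cover PE after retrieval, which stays a secondary measure.
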